### **Laboratory Assessments**

Blood will be collected for laboratory analysis, including Vitamin D, Haematology, WCC differential, C-Reactive protein. Sputum will be collected for microbiological assessment. These samples will be analysed at the local NHS laboratory.

### **Blood Samples for Biomarkers**

Serum blood samples for biobanking will be collected at baseline (attack) and at second visits and stored for future research.

### **Nasal Absorption**

Nasal absorption will be used to collect mucosal lining fluid from the respiratory tract for cytokines profiling at baseline (attack) and at second visits.

### **Nasal Lavage**

Nasal lavage samples will be taken at the baseline (attack) visit. Samples will be obtained by injecting 5ml of sterile normal saline into the participant's nostrils via a nasal adaptor and then

Page 22 of 35

Phenotyping Asthma Exacerbations: A Longitudinal Cohort Study 3 (APEX 3)  
Protocol: Final Version 1.0      10.11.2021      IRAS: 304615

This protocol is confidential and the property of the University of Nottingham. No part of it may be transmitted, reproduced, published, or used by others persons without prior written authorisation from the University of Nottingham

immediately aspirated. These will be placed in a sterile container and transported to the laboratory for viral identification. This procedure will be detailed in a study SOP.

### **Nasal Epithelium Sample**

Nasal brushings samples may be taken at baseline (attack) and at second visits for RNA and DNA extraction. This will be optional and specific consent from participants will be sought. Procedures for sampling and processing will be detailed in a study SOP.

### **Throat Swab**

A throat swab will be taken at the baseline (attack) visit for viral identification.

### **Compliance and adherence**

In order to assess adherence as a factor in exacerbations, a participant's beliefs and attitudes towards medicines will be explored using the Medicines Adherence Report Scale (MARS) questionnaire. Non-intentional non-compliance with usual treatment will be assessed by checking inhaler technique; poor inhaler technique will be reported to the participant's clinical team. Also, GP records will be reviewed for information on medications prescribed in the last 12 months.

Participants who do not attend study visits and then unable to be contacted despite several attempts may be withdrawn from the study.

### **Criteria for terminating trial**

There are no planned criteria for terminating the trial, as we do not anticipate obtaining data or identifying circumstances that would necessitate closing the study early. For individual participants, discontinuation will be considered on a case-by-case basis.

## **TRANSPORT AND STORAGE OF THE TISSUES**

Samples will be labelled in the same format, using study reference, unique patient identifier, time and date taken, and participant visit number.

All biological (blood, sputum, nasal absorption samples and nasal lavage, nasal brushes and throat swabs) samples will be stored in a linked, anonymised format and labelled using a combination of study reference, unique study identifier and cross referenced with location code numbers to permit accurate linkage to study data and the consent form. The master database will be held by the NRRU Database Manager or delegate, in a password encrypted file.

The analysis of samples will either take place in Nottingham, including University of Nottingham premises at Queens Medical Centre and also at the University of Nottingham itself, or in the laboratories of third party national and international partners, following appropriate Tissue Transfer Agreements.

Samples for NHS laboratory analysis (blood samples for haematology, clinical chemistry and sputum for microbiological assessment) will be labelled and analysed in accordance with local NHS procedures.

Once analysis has taken place, blood and sputum samples will be stored at University of Nottingham premises at Respiratory Medicine, The Clinical Sciences Building, Nottingham City Hospital, [name] for future research (DI [name] – Licence Number 12265), if participants are agreeable and sign the optional clause on the consent form.

Where participants do not agree to the future use of the samples, they will be destroyed in accordance with the Human Tissue Act, 2004.

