Description of interventions	

• The collection of medical history, demographic data, and concomitant medications.

• The incidence of upper airway symptoms will be assessed using the Sino-nasal Outcome Test (SNOT).

• The assessment of the incidence of Gastroesophageal Reflux Disease using the GERDQ questionnaire.

• The assessment of the incidence of vocal cord dysfunction using the Pittsburgh Vocal Cord Dysfunction (VCD) Index.

• The assessment of the incidence of dysfunctional breathing using the Nijmegen dysfunctional questionnaire.

• The assessment of the incidence of anxiety and depression using the Hospital Anxiety and Depression Scale (HADS).

• The assessment of the quality of life using the Acute Asthma Quality of Life Questionnaire.

• The assessment of medication adherence using the Medication Adherence Report Scale.

• The assessment of lung function by performing Fractional Exhaled Nitric Oxide (FeNO), Forced Oscillation Technique (FOT), Peak Expiratory Flow Rate (PEFR) and Spirometry.

• The collection of blood samples for laboratory analysis and storage for future research.

• The collection of sputum samples for sputum differential cell count, bacterial culture and sensitivity and storage for future research.

• The collection of nasal absorption samples for future cytokine profiling.

• The collection of samples via nasal lavage and throat swabs for viral identification.

• The collection of optional nasal brushing samples for RNA and DNA extraction.

Duration of study	Study duration: from January 2022 to July 2023.

Randomisation and blinding	Not Applicable

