### SECONDARY OBJECTIVES

- Determine the proportion of patients hospitalised with suspected asthma attacks likely due to non-asthma pathology.
- Describe and assess the incidence of extra-pulmonary co-morbidities in patients hospitalised with asthma attacks.
- Assess incidence of risk factors for attacks based on patients' previous history.
- Assess patients' adherence with asthma medications.
- Compare the use of Forced Oscillation Technique (FOT) as a non-effort dependent measure of airway obstruction in suspected severe asthma attacks to a standard measure of airway obstruction Peak Expiratory Flow Rate (PEFR).
- Compare the use of Fractional Exhaled Nitric Oxide (FeNO) as a measure of airway inflammation against sputum and blood eosinophils.
- Describe objective and symptomatic treatment response and recovery from severe asthma attacks following hospital discharge.

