## STUDY DESIGN

### STUDY CONFIGURATION

This is a single centre observational, longitudinal study. The study will aim to recruit 100 patients hospitalised due to a suspected asthma attack. They will be identified from the Respiratory admission units or inpatient wards at the Nottingham City Hospital or the emergency department at Queens Medical Centre.

The initial assessment will take place at the earliest timepoint possible following hospital admission with a suspected asthma attack. A range of investigations, including lung function tests, blood tests, and questionnaires, will be performed. A follow-up visit will be arranged, which will take place approximately two weeks after hospital discharge at the Nottingham Respiratory Research Unit, at which further lung function tests, blood tests and questionnaires will be performed.

A subsequent telephone follow-up visit will be scheduled at around four weeks after hospital discharge, at which additional questionnaires will be performed to determine the degree of symptomatic recovery. A PhD student will perform the majority of study recruitment and study interventions under the fellow's direct supervision.

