## LABORATORY ANALYSES

Sputum samples will be analyzed at NUH pathology labs for microscopy, culture and sensitivity, following a structured protocol.

Sputum supernatant will be stored in aliquots at -80 degrees centigrade, in monitored and alarmed freezers for future cytokine analysis. Cytospin slides for the differential cell count, will be fixed, stained and counted, before being stored.

Nasal absorption samples will be analyzed in the laboratories of the University of Nottingham.

Samples from nasal lavage and the throat swabs will be analysed in Nottingham, including University of Nottingham premises at Queens Medical Centre and also at the University of Nottingham itself, or in the laboratories of third-party partners, following appropriate Tissue Transfer Agreements.

Samples from nasal brushings will be collected for RNA and DNA extraction and genetic analysis. This will be optional and specific consent from participants will be sought. Sample analysis will take place on University of Nottingham premises. Results of genetic testing will not be shared with participants, however, participants' GP/Consultants will be informed of any incidental findings.

Laboratory analyses will be detailed in a study laboratory manual.

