## STATISTICS

### Methods

Data analysis will be performed by a PhD student, [name], under the supervision of [name], [name] and [name].

The main outcomes of the exacerbation are descriptive in nature, and no statistical tests are planned. We will, however, compare key findings at exacerbation visits with those undertaken at the follow-up visits, including: Paired tests (paired t-test or McNemar) will be used to examine changes in fractional exhaled nitric oxide (FeNO), parameters derived from Forced Oscillation Technique (FOT), the Acute Asthma Quality of Life Questionnaire (Acute AQLQ), sputum differential cell count, nasal absorption, haematology, and clinical chemistry values.

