### **Sample Labelling**

Each participant will be assigned a trial identity code number for use on the samples, consent forms and other study documents and the electronic database. The documents and database will also use their initials (of first and last names separated by a hyphen or a middle name initial when available) and date of birth (dd/mm/yy) and visit.

Samples for NHS pathology analysis will be labelled in accordance with local NHS procedures.

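### Sample labels carry the date and visit number, and the protocol does not provide for counting sputum slides masked to visit, which could bias the attack-to-recovery change

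*Combined protocol and SAP*

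**What the plan says.** **Labels.** Transport and Storage of the Tissues opens with: "Samples will be labelled in the same format, using study reference, unique patient identifier, time and date taken, and participant visit number". Its next paragraph, on stored samples (sputum included), gives a different format: "labelled using a combination of study reference, unique study identifier and cross referenced with location code numbers". Neither visit nor date is listed there. The Sample Labelling section says "Each participant will be assigned a trial identity code number for use on the samples, consent forms and other study documents", then adds initials, date of birth and visit for documents and the database. The exception for NHS laboratory procedures covers sputum for microbiology, not the differential count. Labels on slides are not described separately.

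**Counting.** Laboratory Analyses says: "Cytospin slides for the differential cell count, will be fixed, stained and counted, before being stored". It does not state who counts, whether slides are recoded, in what order they are read, or whether any are read twice. Further detail is left to a laboratory manual, and sputum processing to an SOP. Neither is among the documents.

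**Blinding.** The synopsis has "Randomisation and blinding Not Applicable". The body section headed Randomization and Blinding addresses randomisation only.

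**Use of the count.** The schedule takes sputum at the attack visit and at Day 14 +/-2. The Primary Endpoint section lists the sputum inflammatory cell count at attack and recovery, and gives all its listed measures equal weight. Statistics, Methods includes the sputum differential among the variables for a paired t-test or McNemar test. A secondary objective is to "Compare the use of Fractional Exhaled Nitric Oxide (FeNO) as a measure of airway inflammation against sputum and blood eosinophils", with no method of analysis given.

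**The concern.** A differential cell count is made by a person classifying stained cells, some of them doubtful. If that person knows whether a slide comes from the attack or from recovery, doubtful cells may be classified differently at the two visits. The error then runs along the very contrast the study examines. Analysis cannot remove it afterwards, because it cannot be told apart from a real change, and a larger sample makes it more likely to be declared significant.

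The absence of randomisation does not settle the matter. Masking a reader to visit is useful wherever visits are compared. At stake are the attack-to-recovery change in sputum cells and, under narrower conditions, the comparison of FeNO with sputum eosinophils.

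**Working it through.** The plan states no figure to reproduce. It gives a target of 100 participants and says that no meaningful sample size calculation is possible, so there is no alpha, power, effect size or SD.

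**1. Does the label disclose the visit?** Sputum is taken at two visits only, so the visit number separates attack from recovery. The label format without visit or date is given for stored samples, while counting comes before storage. Of the two formats, the one with the visit number is therefore the more natural reading at the time of counting. That remains an inference, because slide labels are not described.

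**2. What would a visit-linked shift do to the paired test?** Assumptions: true change zero; two-sided alpha 0.05; the reader adds a mean shift of *b* SDs of the paired difference; *n* complete pairs. I take *n* from 30 to 100, because analysis is by complete cases and the number of participants with sputum at both visits is not given. The test statistic is noncentral t with *n* - 1 degrees of freedom and noncentrality *b* x sqrt(*n*). For example, *b* = 0.2 and *n* = 100 give 0.2 x 10 = 2.0. Probability of rejecting:

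| Pairs | b = 0 | b = 0.1 | b = 0.2 | b = 0.3 |
|---|---|---|---|---|
| 30 | 5% | 8.3% | 18.5% | 35.5% |
| 50 | 5% | 10.7% | 28.4% | 54.8% |
| 70 | 5% | 13.1% | 37.8% | 69.7% |
| 100 | 5% | 16.8% | 50.8% | 84.4% |

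The column *b* = 0 is what masked reading in random order is expected to give. The documents offer no evidence of the actual *b*.

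**3. Does it reach the FeNO comparison?** Let the within-visit correlation be *r*, FeNO differ by *d* SDs between visits, the true sputum change be zero, and the reader shift be *b* SDs of sputum within a visit.

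- Within one visit every slide gets the same shift, so the correlation stays at *r*.
- If two equal-sized visits are pooled, the correlation is (*r* + *d b*/4) / sqrt[(1 + *d*²/4)(1 + *b*²/4)]. With *r* = 0.30, *d* = 1 and *b* = 0.3 this is 0.375 / sqrt(1.25 x 1.0225) = 0.33, against 0.27 with no shift. With *r* = 0.50 it is 0.51 against 0.45.
- If changes are correlated, a constant shift again cancels. Only a shift that varies between participants, for example in proportion to the count, could matter.
- If sputum eosinophils were split at a fixed cut-off, a shift at one visit could reclassify slides. The protocol sets no cut-off.

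**4. How many slides?** 100 participants x 2 visits = 200 if everyone gives one slide at each. Repeat admissions, at which attack investigations may be repeated with consent, would add to this.

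**The case against.** The strongest reply is that silence in a protocol is not an unmasked design. Slide labels are not described, one of the label formats omits visit and date, and laboratory detail is deferred to a manual and an SOP that may already require recoding. The synopsis entry is a combined line in a study without allocation, so it need not refer to laboratory reading at all. Samples may also be analysed in University or third-party laboratories, by someone who never meets the patient. All of this stands. It limits the point to what the protocol does not provide for, and a cross-reference would close it if masking is already in the manual.

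It can also be said that the study is descriptive and hypothesis-generating, so little rests on one paired test. That lowers the weight, but a biased count also distorts a description, and inflammatory profile is part of the primary objective.

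Three stronger readings are tempting and are not supported:

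- *That the student who sees the patients also counts the slides.* The protocol says "A PhD student will perform the majority of study recruitment and study interventions" and "Data analysis will be performed by a PhD student". Neither statement assigns slide reading to anyone.
- *That the bias favours the study's hypothesis.* The stated hypothesis is that a significant proportion of these admissions have another cause. The background also notes that many patients receive oral corticosteroid around admission, which markedly lowers confidence in any one expected direction for eosinophils.
- *That agreement of FeNO with sputum eosinophils is inflated.* A visit label does not reveal the FeNO value, and a constant shift per visit leaves the within-visit correlation unchanged.

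**Conclusion.** The point holds as a gap in the protocol. It puts date and visit number on sample labels, has a reader-dependent count made before storage, compares that count between visits, and nowhere provides for masking the reader to visit. Knowledge of the visit could therefore bias the attack-to-recovery change in the sputum differential.

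The size and direction are unknown. Under the stated assumptions a shift of 0.1 SD raises a nominal 5% error to between 8% (30 pairs) and 17% (100 pairs), and 0.2 SD raises it to between 19% and 51%. These figures show how sensitive the comparison is. They do not estimate what will happen.

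A reader might go further and infer that many slides would be misclassified around an eosinophil threshold. The documents give neither a threshold nor a number of cells counted. Assuming 400 cells and 3%, the threshold is 12 cells, and a 10-20% tilt is 1.2-2.4 cells (0.3-0.6 percentage points). That would affect only slides just below the threshold: from 3/1.2 = 2.5% up to 3% at the larger tilt, and from 3/1.1 = 2.7% up to 3% at the smaller.

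The FeNO comparison is touched only if visits are pooled, changes are correlated, a sputum cut-off is applied, or the reader knows the FeNO result. The documents state none of these. The rest of the study is unaffected. The change is worth making because it is cheap and unmasked counts cannot be repaired in analysis.

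**What to change.** In Laboratory Analyses, state that:

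- cytospin slides are recoded without visit number or date before counting, with the code list held by someone other than the reader;
- each participant's attack and recovery slides are counted in random order by a reader without access to visit, FeNO or blood eosinophil results;
- counts are locked before unmasking.

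If the laboratory manual or SOP already requires this, a cross-reference is enough. In Transport and Storage of the Tissues, reconcile the two label formats and say which applies to slides at counting. In the synopsis, limit the not-applicable entry to treatment allocation.

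**Cost.** About 200 slides to relabel, more if repeat attacks are included. Attack counts must wait for the recovery slide, about two weeks after discharge, and attack slides with no recovery partner need a rule, such as being mixed into a batch with other participants' slides. No extra reader is needed if recoding breaks the link to the patient, although whoever recodes takes on a small task. Participants undergo nothing further, and the sample size does not change.

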## LABORATORY ANALYSES

Sputum samples will be analyzed at NUH pathology labs for microscopy, culture and sensitivity, following a structured protocol.

Sputum supernatant will be stored in aliquots at -80 degrees centigrade, in monitored and alarmed freezers for future cytokine analysis. Cytospin slides for the differential cell count, will be fixed, stained and counted, before being stored.

Nasal absorption samples will be analyzed in the laboratories of the University of Nottingham.

Samples from nasal lavage and the throat swabs will be analysed in Nottingham, including University of Nottingham premises at Queens Medical Centre and also at the University of Nottingham itself, or in the laboratories of third-party partners, following appropriate Tissue Transfer Agreements.

Samples from nasal brushings will be collected for RNA and DNA extraction and genetic analysis. This will be optional and specific consent from participants will be sought. Sample analysis will take place on University of Nottingham premises. Results of genetic testing will not be shared with participants, however, participants' GP/Consultants will be informed of any incidental findings.

Laboratory analyses will be detailed in a study laboratory manual.

## STATISTICS

### Methods

Data analysis will be performed by a PhD student, [name], under the supervision of [name], [name] and [name].

The main outcomes of the exacerbation are descriptive in nature, and no statistical tests are planned. We will, however, compare key findings at exacerbation visits with those undertaken at the follow-up visits, including: Paired tests (paired t-test or McNemar) will be used to examine changes in fractional exhaled nitric oxide (FeNO), parameters derived from Forced Oscillation Technique (FOT), the Acute Asthma Quality of Life Questionnaire (Acute AQLQ), sputum differential cell count, nasal absorption, haematology, and clinical chemistry values.

### Sample size and justification

This is an observational, hypothesis-generating study, and due to the lack of previous data on this subject, a meaningful sample size calculation cannot be performed.

## Assessment of safety

An assessment of safety to conduct study procedures will be carried out for each patient prior to recruitment in study and again prior to potential sputum induction. Participants will specifically be asked about the need for further urgent or emergency assessments or treatment for acute asthma at their follow up visit.

## Procedures for missing, unused and spurious data

Values outside the accepted range will be investigated for accuracy. As the focus of this study is descriptive, complete cases analyses will be the primary method for data analysis.

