## **SELECTION AND WITHDRAWAL OF PARTICIPANTS**

### **Recruitment**

Page 16 of 35

Phenotyping Asthma Exacerbations: A Longitudinal Cohort Study 3 (APEX 3)  
Protocol: Final Version 1.0      10.11.2021      IRAS: 304615

This protocol is confidential and the property of the University of Nottingham. No part of it may be transmitted, reproduced, published, or used by others persons without prior written authorisation from the University of Nottingham

Participants will be identified and recruited from admission units or inpatient wards at the Nottingham City Hospital, or the emergency department at Queens Medical Centre. The initial approach will be from a member of the patient's usual care team (which may include the investigator).

The investigator or their nominee, e.g., from the research team or a member of the participant's usual care team, will inform the participant or their nominated representative (other individual or other body with appropriate jurisdiction), of all aspects pertaining to participation in the study.

It will be explained to the potential participant that entry into the trial is entirely voluntary and that their treatment and care will not be affected by their decision. It will also be explained that they can withdraw at any time, but attempts will be made to avoid this occurrence. In the event of their withdrawal, it will be explained that their data collected so far cannot be erased and we will seek consent to use the data in the final analyses where appropriate.

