### Schedule of study assessments.

Visit	Baseline visit	Second visit	Telephone visit
Time	Attack	Day 14 +/-2	Day 28 +/-2
Investigations Performed			
Informed Consent	X		
Medical History	X		
Concomitant Medications	X		
Demographic Data	X		
Sino-nasal Outcome Test	X		
Gastroesophageal Reflux Disease Questionnaire	X		
Pittsburgh Vocal Cord Dysfunction Index	X		
Nijmegen	X		
Hospital Anxiety and Depression Scale	X		
Medication Adherence Report Scale	X		
Inhaler Technique check	X		
Acute Asthma Quality of Life Questionnaire	X	X	X
Spirometry and PEFR	X	X	
Fractional Exhaled Nitric Oxide (FeNO)	X	X	
Forced Oscillation Technique (FOT)	X	X	
Clinical Chemistry (C- Reactive Protein)	X	X	
Sputum (induced or spontaneous) for differential cell count, supernatant storage and microbiological assessment	X	X	
Blood White Cell Count Differential	X	X	
Vitamin D	X		
Viral PCR: Throat swab.	X		
Nasal lavage	X		
Nasosorption Sample	X	X	
Nasal Epithelium Samples for Genetic Analysis (optional)	X	X	

Table 1: Schedule of study assessments.

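### Recovery on the three-visit Acute AQLQ rests on complete-case paired tests, with a complete case undefined; a mixed model using every permitted score, shown beside the paired result, is a cheap improvement

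*Combined protocol and SAP*

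**What the plan says.** The schedule of study assessments (Table 1) lists the "Acute Asthma Quality of Life Questionnaire" at the attack visit, day 14 and the day 28 telephone visit. No other measure is scheduled at all three. Study Configuration explains the telephone visit: "additional questionnaires will be performed to determine the degree of symptomatic recovery". The objective served is the last one under Secondary Objectives: "Describe objective and symptomatic treatment response and recovery from severe asthma attacks following hospital discharge".

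Statistics, Methods, puts description first: "The main outcomes of the exacerbation are descriptive in nature, and no statistical tests are planned". It then makes an exception for change between visits: "Paired tests (paired t-test or McNemar) will be used to examine changes in fractional exhaled nitric oxide (FeNO"), and the list that follows includes the Acute AQLQ. No other method for change is named. The section on missing, unused and spurious data justifies its approach by the descriptive focus: "complete cases analyses will be the primary method for data analysis". No imputation, repeated-measures model or missing-data sensitivity analysis is named.

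Loss is foreseen. Compliance and adherence says: "Participants who do not attend study visits and then unable to be contacted despite several attempts may be withdrawn from the study". Data already collected may remain available: the withdrawal section says they may still be used, and Recruitment says "we will seek consent to use the data in the final analyses where appropriate".

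**The concern.** A paired test compares two time points, but this outcome has three. A participant who misses day 28 drops out of the attack-to-day-28 comparison, although the attack score, and perhaps the day 14 score, is on file and says something about the missing value. If a complete case means all three visits, someone who missed only day 14 drops out of the day 28 comparison too.

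Two things are at stake. One is precision. The other is whom the estimate describes: if participants who return differ in their observed scores from those who do not, the reported recovery belongs to the returners and not to the admitted cohort. That matters in a descriptive study because the estimate is the product.

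**Working it through.** The protocol has no sample size calculation, dropout rate, standard deviation or correlation, so there is no figure to reproduce. From the documents: 100 participants and three Acute AQLQ visits. Everything else below is assumed.

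**1. Scores used.** Take 20% missing at each follow-up, independently.
- Observed scores: 100 + 80 + 80 = 260.
- All three visits required: 100 × 0.8 × 0.8 = 64 participants, 192 scores; 68 of 260 (26%) unused.
- Pairwise: 80 pairs for each contrast.
- If the same 20 people miss both follow-ups, the two readings coincide: 80 participants, 240 scores, 20 of 260 (8%) unused.

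From 10%/15% to 30%/40% missing at day 14/day 28, the three-visit reading leaves 7-45% of observed scores unused.

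**2. Precision.** Simulation at n = 100, 20% or 30% missing completely at random and independently at each follow-up, correlations 0.3-0.7. Variance of the attack-to-day-28 change, relative to maximum likelihood on all scores (unstructured covariance): 1.07-1.16 for pairwise cases and 1.29-1.63 for three-visit cases.

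**3. Shift when loss depends on the attack score and both follow-ups are lost.** Both readings then give the same estimate. Assume means 3.0, 4.6 and 5.0 (change 2.0), SD 1.2, attack-to-follow-up correlation r, and day 14 to day 28 correlation 0.7. Loss is logistic in the standardised attack score Z. Let d = 1.2 × |mean of Z among those retained|. The retained attack mean moves by d and the follow-up mean by r × d, so the change shifts by (1 − r) × d. Numerical integration gives d:

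| Loss | OR 1.5 per SD | OR 2 | OR 3 |
|---|---|---|---|
| 10% | 0.048 | 0.079 | 0.117 |
| 20% | 0.095 | 0.155 | 0.223 |
| 30% | 0.141 | 0.228 | 0.324 |

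At r = 0.4 the shift is 0.6 × d: 0.03-0.07, 0.06-0.13 and 0.08-0.19 at 10%, 20% and 30% loss. The estimated change is too small if low scorers are lost and too large if high scorers are.

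Standard error = 1.2 × √(2 × 0.6) / √(100 × (1 − loss)) = 0.139, 0.147 and 0.157. The largest ratios are 0.070/0.139 = 0.5, 0.134/0.147 = 0.9 and 0.194/0.157 = 1.2.

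Over r = 0.2-0.6 the shift runs from 0.4 × 0.048 = 0.02 to 0.8 × 0.324 = 0.26. At r = 0.2 it also slightly passes one standard error at 20% loss and OR 3: 0.178/0.170 = 1.05.

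The likelihood estimate stays within 0.003 of the truth. Simulated coverage of the 95% interval at r = 0.4 is 92-94%, 85-93% and 76-92% for the paired analysis at the three loss rates, against about 95% for likelihood.

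**4. Only day 28 lost, depending on the day 14 score (r = 0.4).** The day 28 mean moves by 0.7 × d and the attack mean by 0.4 × d, a net 0.3 × d: from 0.01 (10%, OR 1.5) to 0.10 (30%, OR 3). Likelihood is within 0.001.

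**5. Mixed patterns.** Day 14 loss depends on the attack score; day 28 loss depends on the day 14 score, or on the attack score if day 14 is missing. With about 24-36% missing per visit, bias in SD units is 0.06-0.10 for three-visit cases, 0.00-0.03 for pairwise cases and at most 0.01 for likelihood.

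**6. Limit: loss depends on the unseen day 28 score.** Bias at 30% loss, OR 1.5-3:

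| Setting | Paired | Likelihood |
|---|---|---|
| r 0.4, both follow-ups lost | 0.08-0.19 | 0.12-0.28 |
| r 0.4, day 14 seen | 0.08-0.19 | 0.07-0.17 |
| r 0.6, day 14 seen | 0.06-0.13 | 0.07-0.16 |

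In the first row at OR 3, coverage is 75% for the paired test and 53% for likelihood.

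**The case against.** The protocol gives a reason for complete cases: the study is descriptive and hypothesis-generating, has no endpoints, and places recovery last among seven secondary objectives. Calling the method primary does not exclude a supplementary analysis. Attack scores of people lost later still enter the attack description, which is the primary objective. All of this stands, and it makes the plan's choice defensible rather than an error.

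The pairwise reading is natural for paired tests, and under it the cost is modest: steps 2 and 5 give a 7-16% variance penalty and little bias under mixed loss. A reader might infer that the plan throws away up to 45% of the scores. The documents do not support that, because the figure needs the three-visit reading and heavy, scattered missingness, and the protocol states neither.

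The strongest objection is that the mixed model can do worse. Participants who cannot be reached may be missing because of how they are recovering, and step 6 then favours the paired test whenever both follow-ups are lost. Having a day 14 score does not rescue the model in general: it is slightly closer than the paired test at r of 0.4 or below, but further off at about 0.6. This stands. It argues for showing both estimates, not for leaving the paired test alone.

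**Conclusion.** The point holds as a cheap improvement that should be made. Complete case is undefined, and under either definition a missed visit keeps some observed Acute AQLQ scores out of the recovery estimate. The variance cost is about 7-16% if pairwise and 29-63% if all three visits are required (20-30% missing, independent across visits). If loss depends on observed scores, the day 28 change shifts by about 0.01-0.26 points over 10-30% loss, odds ratios 1.5-3 and r 0.2-0.6, against an assumed change of 2.0. That is usually less than one standard error, its direction cannot be known in advance, and likelihood nearly removes it. Every input except the 100 participants and the visit schedule is assumed.

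Two stronger conclusions are tempting and not supported. One is that the recovery result would be invalid: no confirmatory test rests on it, and the shift is small in most settings. The other is that a mixed model is always the better estimate: that depends on missing at random, which the documents neither state nor contradict.

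**What to change.** - Analyse the Acute AQLQ with a likelihood-based mixed model over the three visits: visit categorical, unstructured within-participant covariance. Include every score whose use is permitted under the Recruitment and withdrawal sections.
- Report the attack-to-day-14 and attack-to-day-28 contrasts with intervals.
- Report the paired analysis beside it, and state that complete cases are defined pairwise.
- Tabulate attack scores for participants with and without each follow-up.
- State that neither estimate is unbiased if loss depends on unseen recovery, and that the model may then be further off than the paired test.

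Cost: one model for one questionnaire, one table and a few sentences; no new visits or tests. The price is a little more analysis work and a missing-at-random assumption, which is why the paired result stays in view.
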